4.2.3 Rationale for Endpoints

Here we propose a clinical trial testing the hypothesis that the administration of pembrolizumab in the presence of gut microbiota manipulation with EDP1503 will increase the depth of response in patients who are naïve to PD1 antibody and may induce response in patients who have previously progressed on anti-PD1 antibody. In addition the trial will test the hypothesis that EDP1503, as monotherapy, is safe and that any adverse effects are consistent with historical observations of probiotic therapy, such as mild and transient GI disturbance.

The rationale for the primary endpoints in each cohort stem from the intersection of trial feasibility, meaningful clinical patient outcomes and the early nature of investigation surrounding the impact of the microbiome on anti-tumor immunity. Sample size calculations for analysis of a substantial improvement in the response rate in the PD1 naïve population make the analysis of standard RECIST response rate not feasible in a modestly sized phase II study. Randomized designs were also considered though were not supported by the pharmaceutical sponsor in the modestly sized phase II setting. Simultaneously it has been recognized in the melanoma community that quality of response to treatment is particularly meaningful as patients who have deep responses rarely recur²¹⁻²³. In fact multiple groups are proposing randomized studies to investigate early discontinuation of PD1 after maximum response while the Canadian government has launched such a trial²⁴. In this context the primary end point for cohort 1 was chosen as deep response (> 80%) as this level of response has been observed consistently in approximately 40% of patients in combination clinical trials of the anti-PD1 antibody (nivolumab) in combination with anti-CTLA4 antibody

(ipilimumab). This deep response rate has been published in the New England Journal of Medicine four times across the phase I CA209-004²⁵, phase II CHECKMATE-069²⁶ and phase III CHECKMATE-067 studies^{27,28}. In cohort 2 the primary endpoint is improvement in RECIST response as is commonly used. In this refractory cohort no responses are normally expected thus facilitating a straightforward Simon two-stage design.

Prior investigations regarding the modulation of the gut flora in preclinical melanoma models demonstrated that this effect restored partial tumor control however the addition of PDL1 antibody completely ablated tumors. Through our correlative analysis, we hope to propose a model by which we can suggest which patients would benefit from pembrolizumab alone or pembrolizumab in the presence of gut microbiota manipulation with EDP1503 or other probiotic.

4.2.3.1 Efficacy Endpoints

The primary efficacy objective of this trial is to evaluate the anti-tumor activity of pembrolizumab in the presence of gut microbiota manipulation with EDP1503 in subjects with advanced melanoma who are naïve or refractory to anti-PD1 antibody.

RECIST as assessed by the investigator will be used as the primary response rate efficacy endpoint however irRC will also be followed. RECIST will also be used by the local site to determine eligibility and make treatment decisions. The primary efficacy endpoint is response rate based on RECIST. Secondary endpoints are listed in section 3.2.

Immunotherapeutic agents such as pembrolizumab may produce antitumor effects by potentiating endogenous cancer-specific immune responses which may be functionally anergic. The response patterns seen with such an approach may extend beyond the typical time course of responses seen with cytotoxic agents, and can manifest a clinical response after an initial increase in tumor burden or even the appearance of new lesions. Standard RECIST criteria may not provide a complete response assessment of immunotherapeutic agents such as pembrolizumab therefore the irRC have been developed to encompass this.

Broadly, irRC includes the concept of treatment beyond progression, if radiologic imaging shows PD, tumor assessment should be repeated ≥ 4 weeks later in order to confirm PD with the option of continuing treatment per below while awaiting radiologic confirmation of progression. If repeat imaging shows a reduction in the tumor burden compared to the initial scan demonstrating PD, treatment may be continued as per treatment calendar. If repeat imaging confirms progressive disease, subjects will be discontinued from trial therapy. In determining whether or not the tumor burden has increased or decreased, Investigators should consider all target lesions as well as non-target lesions.

In subjects who have initial evidence of radiological PD, it is at the discretion of the treating physician whether to continue a subject on study treatment until repeat imaging is obtained a minimum of 4 weeks later. This decision should be based on the clinical judgment of the subject's overall clinical condition, including performance status, clinical symptoms, and laboratory data. Subjects may receive treatment while waiting for confirmation of PD if they are clinically stable as defined by the following criteria:

• Absence of signs and symptoms indicating disease progression

- No decline in ECOG performance status
- Absence of rapid progression of disease
- Absence of progressive tumor at critical anatomical sites (e.g., cord compression) requiring urgent alternative medical intervention

When feasible, subjects should not be discontinued until progression is confirmed. This allowance to continue treatment despite initial radiologic progression takes into account the observation that some subjects can have a transient tumor flare in the first few months after the start of immunotherapy, but with subsequent disease response. Subjects that are deemed clinically unstable are not required to have repeat imaging for confirmation of progressive disease.

4.2.3.2 Biomarker Research

Our group has previously described the T cell-inflamed tumor microenvironment as a potential predictive biomarker for response to multiple immunotherapies including therapeutic vaccines, anti-CTLA-4, and anti-PD-1/PD-L1 antibodies⁴⁻¹⁰. Our analysis of the tumor microenvironment in patients with melanoma suggests that approximately 35-50% of cases show evidence of spontaneous priming of anti-tumor T cells leading to migration of CD8+ effector T cells into tumor sites. This phenotype has been designated the T cell-inflamed tumor microenvironment and is characterized by expression of T cell markers, chemokines for T cell recruitment, and transcripts indicative of type I IFN signaling^{5,6,8}.

In addition to response prediction, this gene signature is also potentially useful in identifying those that will not respond. Patients harboring non-inflamed tumors therefore require treatment strategies which may modulate the immune response to facilitate the influx of tumor infiltrating lymphocytes (TIL) and conversion from a non-inflamed to an inflamed tumor.

Beyond the tumor microenvironment, aspects of the host (patient) and commensal environment may also have an essential impact on immunity in response to both radiation and anti-PD1 antibody. Host factors of interest regarding the immune response include circulating immune subsets as well as germline DNA sequence and polymorphisms. Further, a growing literature supports a role for commensal microbiota in the immune response to infection and cancer including development of acute versus chronic immune responses and regulatory mechanisms to prevent collateral tissue damage¹¹. We and others have proposed that manipulation of the microbiome has the potential ability to modulate the anti-tumor immune response and promote the development of an inflamed tumor microenvironment^{12,13}.

Considering this background, we propose to collect peripheral blood for serum, peripheral blood mononuclear cells, germline DNA, as well as fecal samples throughout treatment. **Baseline tumor tissue prior to treatment and/or fresh tumor biopsy at baseline and at after EDP1503 run-in are required on all patients**. Diagnostic tissue from prior biopsy is allowed if the tissue was obtained by core or surgical biopsy (FNA is not acceptable) and no intervening systemic treatment has been administered. Peripheral blood for serum and blood mononuclear cells will be taken at the beginning and end of the run in period when subjects are only taking EDP1503 to evaluate any immediate effects on these biomarkers. Tumor

biopsy will be required at the end of the second week of EDP1503 run-in (prior to starting pembrolizumab) in patient's naïve to anti-PD1 (cohort 1) unless considered not clinically feasible. These biopsies will be analyzed to evaluate the effect of the EDP1503 on the tumor microenvironment.

Fecal samples will be analyzed by a variety of methods to determine quantitatively if there is a correlation between specific features of the host microbiome and/ or its manipulation with the effect on the systemic and tumor biomarkers. Analysis may include microbial culturing and nucleic acid based evaluation. Micro-organisms cultured from patient fecal samples may be stored and studied in preclinical models with the intent of learning more about the interaction between the microbiome and host immune responses.

Additionally, it is requested that any patients who undergo tumor biopsy as part of their standard care during the study have any available tissue forwarded for analysis in comparison of pre-administration and on-/post-treatment tumor microenvironmental factors.

5.0 METHODOLOGY

5.1 Entry Criteria

5.1.1 Diagnosis/Condition for Entry into the Trial

1. Advanced, unresectable or metastatic melanoma

	1.5 ULN
AST (SCOT) and ALT (SCDT)	≤ 2.5 X ULN OR
AST (SGOT) and ALT (SGPT)	≤ 5 X ULN for subjects with liver metastases
Albumin	≥2.5 mg/dL
^a Creatinine clearance should be calculated p	per institutional standard.

- 7. Female subject of childbearing potential should have a negative urine or serum pregnancy within 72 hours prior to receiving the first dose of study medication. If the urine test is positive or cannot be confirmed as negative, a serum pregnancy test will be required.
- 8. Female subjects of childbearing potential (Section 5.7.2) must be willing to use an adequate method of contraception as outlined in Section 5.7.2 Contraception, for the course of the study through 120 days after the last dose of study medication.

Note: Abstinence is acceptable if this is the usual lifestyle and preferred contraception for the subject.

9. Male subjects of childbearing potential (Section 5.7.1) must agree to use an adequate method of contraception as outlined in Section 5.7.1- Contraception, starting with the first dose of study therapy through 120 days after the last dose of study therapy.

Note: Abstinence is acceptable if this is the usual lifestyle and preferred contraception for the subject.

5.1.3 Subject Exclusion Criteria

The subject must be excluded from participating in the trial if the subject:

- 1. For cohort 2: Has BRAF mutant disease but has not yet received treatment with RAF/MEK inhibitors.
 - This criteria can be met via adjuvant treatment with BRAF-MEK inhibitors
- 2. Is currently participating and receiving study therapy or has participated in a study of an investigational agent and received study therapy or used an investigational device within 2 weeks of the first dose.
- 3. Is currently taking Bifidobacterium based probiotics or is taking pre/pro-biotics regularly.
- 4. Has a diagnosis of immunodeficiency or is receiving systemic steroid therapy or any other form of immunosuppressive therapy within 7 days prior to the first dose.
- 5. Has a known history of active TB (Bacillus Tuberculosis)
- 6. Hypersensitivity to pembrolizumab or any of its excipients.
- 7. Has had a prior anti-cancer monoclonal antibody (mAb) within 3 weeks prior to study Day 1 (excluding anti-PD1 antibodies such as pembrolizumab or nivolumab in cohort 2) or who has not recovered (i.e., ≤ Grade 1 or at baseline) from adverse events due to agents administered more than 4 weeks earlier.
- 8. Has had prior chemotherapy, targeted small molecule therapy, or radiation therapy within 2 weeks prior to study Day 1 or who has not recovered (i.e., ≤ Grade 1 or at baseline) from adverse events due to a previously administered agent.
 - Note: Subjects with ≤ Grade 2 neuropathy are an exception to this criterion and may qualify for the study.
 - Note: If subject received major surgery, they must have recovered adequately from the toxicity and/or complications from the intervention prior to starting therapy.
- 9. Has a known additional malignancy that is progressing or requires active treatment. Exceptions include basal cell carcinoma of the skin or squamous cell carcinoma of the skin that has undergone potentially curative therapy or *in situ* cervical cancer.
- 10. Has known active central nervous system (CNS) metastases and/or carcinomatous meningitis. Subjects with previously treated brain metastases may participate provided they are stable (without evidence of progression by imaging for at least four weeks prior to the first dose and any neurologic symptoms have returned to baseline), have no evidence of new or enlarging brain metastases, and are not using steroids for at least 7 days prior to start of study. This exception does not include carcinomatous meningitis which is excluded regardless of clinical stability.

- 11. Has active autoimmune disease that has required systemic treatment in the past 2 years (i.e. with use of disease modifying agents, corticosteroids or immunosuppressive drugs). Replacement therapy (eg., thyroxine, insulin, or physiologic corticosteroid replacement therapy for adrenal or pituitary insufficiency, etc.) is not considered a form of systemic treatment.
- 12. Has known history of, or any evidence of active, non-infectious pneumonitis.
- 13. Has an active infection requiring antibiotic therapy or has received a course of antibiotics within the previous 2 weeks of starting study treatment.
- 14. Has a history or current evidence of any condition, therapy, or laboratory abnormality that might confound the results of the trial, interfere with the subject's participation for the full duration of the trial, or is not in the best interest of the subject to participate, in the opinion of the treating investigator.
- 15. Has known psychiatric or substance abuse disorders that would interfere with cooperation with the requirements of the trial.
- 16. Is pregnant or breastfeeding, or expecting to conceive or father children within the projected duration of the trial, starting with the screening visit through 120 days after the last dose of trial treatment.
- 17. Has a known history of Human Immunodeficiency Virus (HIV) (HIV 1/2 antibodies).
- 18. Has known active Hepatitis B (e.g., HBsAg reactive) or Hepatitis C (e.g., HCV RNA [qualitative] is detected).
- 19. Has received a live vaccine within 30 days of planned start of study therapy.

Note: Seasonal influenza vaccines for injection are generally inactivated flu vaccines and are allowed; however intranasal influenza vaccines (e.g., Flu-Mist®) are live attenuated vaccines, and are not allowed.

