3.3 Exploratory Objective

(1) **Objective**: Assessment of whether the administration of EDP1503 alters immune cell phenotypes in the tumor microenvironment.

Hypothesis: Oral administration of EDP1503 will result in changes in the immune cell phenotypes in the tumor microenvironment

(2) **Objective**: Assessment of fecal material for bacterial contents

Hypothesis: Oral administration of EDP1503 will result in increased level of EDP1503 in the fecal contents

(3) **Objective:** Biospecimen collection throughout the study including microbiota contents, peripheral blood and tumor tissue.

Hypothesis: Oral administration of EDP1503 will result in changes in immune cell phenotypes detectable in the systemic circulation

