Pembrolizumab is a potent and highly selective humanized monoclonal antibody (mAb) of the IgG4/kappa isotype designed to directly block the interaction between PD-1 and its ligands, PD-L1 and PD-L2. KeytrudaTM (pembrolizumab) has recently been approved in the United States for the treatment of patients with unresectable or metastatic melanoma and disease progression following ipilumumab and, if BRAF V600 mutation positive, a BRAF inhibitor.

Bifidobacteria are a gram positive, anaerobic, non-spore forming, rod shaped genus of bacteria (Weber et al 2015). They are naturally found in the colon of healthy humans and animals throughout early life and into adulthood (O'Callaghan et al 2016). Bifidobacterium are frequently used in foods and supplements in North America and Europe and these strains in food products have been designated 'Generally Regarded As Safe' (GRAS, 21 CFR 170; FDA GRAS Notices) or 'Qualified Presumption of Safety' (QPS) Status (EFSA) along with many other lactic acid producing bacteria. These bacteria are found in fermented foods, yogurts, supplements, and other foodstuffs at levels between 1x10⁹- 1x10¹¹ CFU/serving (FDA GRAS Notices, EFSA Journal 2013). These strains are selected to impart beneficial health effects on the host and positively impact the host gut microbiota composition, metabolism, and general health without adverse changes to the gut (O'Callaghan et al 2016). Many of them are originally isolated from healthy hosts and are ubiquitous in the diet and the healthy large

intestine of humans soon after birth throughout life. They have been evaluated in 100s of clinical trials (854 references on PubMed of "clinical trials Bifidobacterium") in subjects ranging from preterm infants to elderly adults with minimal adverse events.

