Thereafter we have pursued a detailed investigation of the microbial contents of the fecal material from Jackson mice as compared with Taconic. In concert with colleagues at the Argonne National Laboratory, 16S ribosomal sequencing identified a small number of bacterial species that were significantly different between these strains. The top candidate was the genus Bifidobacterium. Using commercial sources, we obtained a probiotic consisting of only Bifidobacterium species for preclinical experimentation. In fact, administration of two weekly doses of Bifidobacterium was sufficient to exert anti-tumor activity in C57BL/6 mice from Taconic, which synergized with anti-PD-L1 mAb to cause complete tumor elimination in most animals. After an intensive screening process, Evelo Biosciences identified a strain of Bifidobacterium animalis lactis with consistently high performance in tumor isograft assays including B16 melanoma, and manufactured this strain under GMP into a drug product known as EDP1503.

These data provide evidence implicating the microbiota in shaping anti-tumor immunity and provide a rationale for a clinical trial evaluating the efficacy of pembrolizumab in the presence of gut microbiota manipulation with EDP1503.

In summary, our data suggest that the intestinal microbiota have a significant impact on antitumor immunity and see the potential of specific microorganisms to modify the commensal environment of the host and enhance the anti-tumor effect of anti-PD-1. We therefore propose a phase II study evaluating the efficacy of pembrolizumab in the presence of gut microbiota manipulation with EDP1503 in subjects with advanced melanoma who are either naïve or refractory to anti-PD1 antibody treatment.

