A fixed dose regimen will simplify the dosing regimen to be more convenient for physicians and to reduce potential for dosing errors. A fixed dosing scheme will also reduce complexity in the logistical chain at treatment facilities and reduce wastage.

The landscape of adjuvant therapy options for high risk cutaneous melanoma is in a state of flux and treatments that recently formed the backbone of systemic therapy for metastatic disease are now being used earlier. Whereas interferon-α and more recently ipilimumab were standards of care (PMID: 23042723, PMID: 27717298), patients with high risk stage III melanoma now have standard of care options with combination BRAF-MEK inhibition and anti-PD1 antibody. In a phase III study of dabrafenib and trametinib compared with placebos, estimated 3 year relapse-free survival was 58% in the treatment group versus 39% for placebo with the hazard ratio for relapse or death of 0.47 (95% confidence interval [CI], 0.39 to 0.58; P<0.001) (PMID: 28891408). In a phase III study of nivolumab compared with ipilimumab relapse free survival at 12 months was 71% with nivolumab as compared with 61% for ipilimumab with a hazard ratio for relapse or death of 0.65 (97.56% CI, 0.51 to 0.83; P<0.001) (PMID: 28891423). Given these data many patients diagnosed with advanced disease will have previously been treated with PD1 based therapy and approaches that augment systemic immunity to facilitate clinical response in the setting of resistance are of high priority.

EDP1503

Amounts of Bifidobacterium consumed by humans in various commercially available Bifidobacterium-based probiotics range from 1×10^9 to 3.6×10^{12} CFU^{15,16} The Bifidobacterium capsule in this study will contain >7.5x10¹⁰ CFU/capsule and will be taken at an amount of 2 capsules bid for a total of 4 capsules per day, half in the morning and half in the evening.

Foods containing Bifidobacterium have been consumed by millions of people largely with a lack of side effects. Minor adverse events include bloating, flatus, loose stool, and mild gastrointestinal discomfort. In extremely rare cases, lactic acid bacteria based probiotics have been identified as the cause of bacteremia but generally pose far less threat than one's own gastrointestinal flora^{17,18}. Patients who have experienced Bifidobacterium bacteremia are usually immunocompromised and severely sick¹⁹. In a majority of these cases, antibiotic

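### Exclusion 3 sets no look-back for probiotic use, so baseline stool, blood and fresh-biopsy samples may reflect recent Bifidobacterium exposure

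*Combined protocol and SAP*

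**What the plan says.** Section 5.1.3, item 3, excludes a patient who "Is currently taking Bifidobacterium based probiotics or is taking pre/pro-biotics regularly". Item 13 of the same list excludes anyone with an active infection needing antibiotics, and anyone who "has received a course of antibiotics within the previous 2 weeks of starting study treatment".

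Three other provisions touch on earlier probiotic use:

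- Section 5.5.2 prohibits other dietary probiotics and prebiotics, but only during screening and treatment.
- Section 8.1.1.4.1 has prior medication recorded for the 28 days before the trial starts.
- Item 14 of section 5.1.3 lets the treating investigator exclude a patient for a past therapy that could confound the results.

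The flow chart (section 6.1) puts screening at day -21 to -1. Baseline stool and correlative blood are collected in that window. Section 8.1.1.11 lists pre-EDP1503 stool, mononuclear cells, cytokines, blood culture and an EDP1503 PCR.

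One exploratory hypothesis in section 3.3 is that "Oral administration of EDP1503 will result in increased level of EDP1503 in the fecal contents". Section 10.1 tests whether the tumor inflammation signature (TIS) changes between paired biopsies.

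**The concern.** The exploratory questions ask what changes between baseline and the end of the EDP1503 run-in. There is no randomization and no untreated group, so each patient's own baseline is the main comparator. A baseline sample taken soon after another Bifidobacterium product may already show part of the effect being looked for, and the measured change would then be too small.

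The rationale gives some reason to take this seriously. Section 4.2.1 reports that in mice "administration of two weekly doses of Bifidobacterium was sufficient to exert anti-tumor activity", using a commercially sourced product before the EDP1503 strain was selected. The flow chart footnotes allow the second biopsy after at least 10 days of EDP1503 in cohort 1 and at least 4 days in cohort 2, so the design itself looks for effects within days.

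What is at stake is how the run-in comparisons of microbiome, immune markers and TIS are read. A baseline sample taken after recent use cannot be corrected later.

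**Working it through.** **1. Does any rule close the gap?**

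| Rule | Reach | Closes it? |
|---|---|---|
| 5.1.3 item 3, first half | Current Bifidobacterium use | No, present tense |
| 5.1.3 item 3, second half | Regular pre/probiotic use | No, also present tense |
| 5.5.2 | From screening on | No, nothing earlier |
| 8.1.1.4.1 | 28 days, recorded | No, excludes no one |
| 5.1.3 item 14 | Investigator's opinion | Not reliably: no interval, probiotics not named |
| 5.1.3 item 13 (comparison) | 2 weeks | Antibiotics only |

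A long-term user who stops the day before screening breaches no explicit rule.

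**2. How soon can the baseline sample follow?** Suppose screening opens on day -21 and last use was on day -22. A sample on day -21 comes 1 day after last use, and one on day -1 comes 21 days after. The plan leaves that gap to scheduling.

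**3. Scale of other products against the trial dose.** Section 4.2.2 says the capsule "will contain >7.5x10¹⁰ CFU/capsule and will be taken at an amount of 2 capsules bid for a total of 4 capsules per day".

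- Reproducing the intake: 2 capsules x 2 = 4 per day, and 4 x 7.5x10^10 = 3.0x10^11 CFU per day. This is a floor, because potency is given as greater than.
- Section 4.2.2 says amounts in commercial "Bifidobacterium-based probiotics range from 1×10^9 to 3.6×10^{12} CFU". Top: 3.6x10^12 / 3.0x10^11 = 12. Bottom: 1x10^9 / 3.0x10^11 = 0.0033, or 0.33%.
- Section 4.1.1 places fermented foods, yogurts, "supplements, and other foodstuffs at levels between 1x10⁹- 1x10¹¹ CFU/serving". Top: 1x10^11 / 3.0x10^11 = one third, so three such servings a day would match the trial floor.

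The section 4.2.2 range has no time unit, so comparing it with a daily dose is an assumption. Recent exposure could range from negligible to above the trial dose.

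**4. Effect on the paired change.** Let δ be the true mean change in unexposed patients, q the share of recent users, and c the part of the effect already present in their baseline. Then the mean change is (1 - q)δ + q(1 - c)δ = (1 - qc)δ. Neither q nor c is in the documents. Assuming q of 5% to 20%, which is 1.75 to 7 of 35 patients:

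- c = 1 (no further change): the mean change shrinks by 5% to 20%.
- c = 0.5 (illustrative): it shrinks by 2.5% to 10%.
- c = 0 (no carry-over): no effect.

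**5. Efficacy rules.** In cohort 1, success is 4 or more deep responses in 35. The exact probability of that is 0.096 at a true rate of 0.05 and 0.939 at 0.20, within the planned 0.1 and 0.1 error limits. In both cohorts the rule counts tumor responses; no baseline stool, blood or TIS value enters.

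**6. Would a 2-week interval fit?** A patient who stops on day -21 completes 14 days on day -7. That leaves day -7 to day -1 for prospective baseline samples.

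**The case against.** The strongest case against is that the gap is narrow and partly covered. Regular users up to the day of screening are the people item 3 is aimed at, section 5.5.2 stops further use, item 14 gives the investigator a way to exclude, and the 28-day record may already identify recent users. The affected analyses are exploratory, and section 10.1 treats microbial data descriptively. All of this limits the consequence. It does not supply an interval: a discretionary clause that does not name probiotics may be applied differently by different sites, and a record excludes no one.

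A reader might infer more than the documents support:

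- **That baseline samples already contain the intervention.** EDP1503 is one cloned strain (section 4.2.2). Another product would leave Bifidobacterium, not necessarily that strain. The documents do not state how specific the PCR is or how long other strains persist. The mouse result shows an effect of dosing, not of carry-over.
- **That recent users will typically have matched or exceeded the trial dose.** The ratio of 12 uses the top of a range without a time unit; one serving at the section 4.1.1 maximum is a third of the daily floor.
- **That probiotics are the only relevant exposure without a washout.** Item 7 waives the antibody washout for prior anti-PD1 in cohort 2. The sound comparison is with antibiotics.
- **That a null result would be uninterpretable.** On the assumed shares, 80% to 95% of patients would be unaffected.

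**Conclusion.** The point holds in a limited form. No probiotic look-back exists in the documents, antibiotics have one, and a recent user can enrol and give baseline stool, blood and fresh-biopsy samples that may reflect recent Bifidobacterium exposure. The likely consequence is bias in the exploratory baseline-to-run-in comparisons, usually toward no change.

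The direction is not certain in every case. Cohort 1 may use archival tissue (flow chart footnote d). If that tissue predates the probiotic use, part of the other product's effect could be credited to EDP1503.

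The size is not known. The 5% to 20% shrinkage rests on an assumed share of recent users and on full carry-over. The primary efficacy rules, their error rates and the sample size are not affected. The change is still worth making, because it is cheap and the bias cannot be removed after sampling.

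**What to change.** Reword item 3 to exclude any Bifidobacterium-based product, or regular pre/probiotic use, within a stated interval before the first prospectively collected baseline sample. Except archival tissue explicitly; otherwise the interval would run back from a specimen that may long predate screening.

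Two weeks is a workable choice by analogy with item 13, and it fits the 21-day screening window. It should be labelled an assumption, since the documents give no persistence time and item 13 is anchored to the start of treatment, not to sampling.

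Also:

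- allow patients who stop to be re-screened after the interval;
- record the date of last probiotic use, including for patients with archival tissue;
- add to section 10.1 a sensitivity analysis of the paired comparisons that leaves out recent users.

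The cost is one phrase in item 3, one date field and one short analysis paragraph. The downside is that a few probiotic users may start up to about 2 weeks later.
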